#### **Maximum Tumor Burden Decrease**

Tumor burden is defined as the sum of the diameters (longest for non-nodal lesions, short axis for nodal lesions) for all target lesions and up to 10 (maximum 5 per organ) new measurable lesions. Tumor burden ratio is defined as the ratio of the tumor burden at each assessment divided by the baseline tumor burden. The Maximum tumor burden decrease is defined as smallest tumor burden ratio among all assessments -1.

The maximum tumor burden decrease at the subject-level will be censored **at the earliest after the start of the first subsequent anticancer therapy, or on or after the event of** complete or partial removal/reduction of any target lesion which contained cancer on pathology evaluation or pathology results were unknown.

The maximum tumor burden decrease at the lesion-level will be censored at the earliest after the start of **the first subsequent anticancer therapy**, or on or after the event of merging with another lesion, or complete or partial removal/reduction of any target lesion which contained cancer on pathology evaluation or pathology results were unknown. If a lesion splits, the sum of the length of the split lesions will be added together prior to analysis.

### **Overall Survival (OS)**

Overall survival (OS) is defined as the time from the date of first dose date to the date of death from any cause. Death is the event of interest. OS time will be censored at the last date the patient is known to be alive when the confirmation of death is absent or unknown.

### **Evaluable tumor assessment**

An overall visit response other than unevaluable (UE) or not done (ND).

### **Evaluable lesion**

A target lesion or a new measurable lesion with a baseline and at least subsequent non missing dimension.

### **Progression-free survival (PFS)**

PFS is defined as the interval from first dose date to the earlier event of confirmed PD or death from any cause. Subjects without an event will be censored at the latter of their last evaluable tumor assessment if available; otherwise will be censored on Study Day 1.

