Local palliative radiation treatment for relief of various symptoms, including but not limited to bleeding or pain associated with the underlying disease will be permitted at any time during the study. Subjects with local symptoms suggestive of disease progression should be evaluated for tumor response per modified irRC-RECIST (see [Appendix D](#)) prior to the administration of palliative radiotherapy. If a subject undergoes local radiation, the investigator or designee should notify the sponsor medical monitor as soon as possible and the treatment should be recorded in the source document and CRF.

If a subject demonstrates evidence of new or worsening CNS metastases, talimogene laherparepvec and/or pembrolizumab treatment should be withheld and the investigator or designee should notify the sponsor's medical monitor as soon as possible. Subjects may be allowed to remain on study after discussion between the sponsor medical monitor and the investigator to determine the appropriateness of treatment resumption provided CNS lesions can be treated with stereotactic radiotherapy (including Gamma Knife), whole brain radiation, or craniotomy and if there is no change in the baseline ECOG performance status. Subjects may be allowed to resume talimogene laherparepvec treatment per Section 6.2.1 following treatment of CNS metastases while receiving dexamethasone or a similar corticosteroid at no more than 1.5 mg dexamethasone (or 10 mg prednisone) per day. If higher doses of corticosteroid are used, talimogene laherparepvec must be held until that dose level is reached during the period of steroid tapering.

If a subject with confirmed PD (ie, two consecutive tumor assessments at least 4 weeks [28 days] apart demonstrating PD) is clinically stable or clinically improved, and there is no further increase in tumor burden at the confirmatory assessments (assessed by the

investigator and site radiologist, if applicable), an exception may be considered to continue treatment upon consultation with the sponsor medical monitor.

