6.9 Excluded Treatments and/or Procedures During Study Period

Subjects must not use any of the following therapies during screening or treatment period (including retreatment for post-CR relapse) of this trial:

- investigational agents (other than pembrolizumab and talimogene laherparepvec) or procedures
- warfarin. Other anticoagulants (ie. low molecular weight heparins, non-steroidal anti-inflammatory drugs) that do not prolong the PT/INR may be administered after investigator discussion with the sponsor and as long as there is adherence to institutional guidelines requiring their withholding for interventional radiology procedures.
- concurrent experimental or approved anti-tumor therapies or biological therapy other than study drug and radiation therapy required for palliation (as noted in Section 6.5)

Note: Radiation therapy to a symptomatic solitary lesion or to the brain may be considered on an exceptional case by case basis after consultation with Sponsor. The subject must have clear measurable disease outside the radiated field. Administration of palliative radiation therapy will be considered clinical progression for the purposes of determining PFS.

- immunotherapy not specified in this protocol
- chemotherapy not specified in this protocol

- chronic oral or systemic steroid medication use at a dose of >10 mg/day of prednisone (1.5 mg/day dexamethasone) or equivalent (with the exception of treatment for adverse events [see Section 6.2.1.2] and CNS metastases [see Section 6.5]). Steroids with low systemic absorption [eg, triamcinolone hexacetonide] injected into a joint space, and intermittent use of steroid inhalers or topical steroid is allowed).
- antiherpetic drugs, except those topically administered
- live vaccines within 30 days prior to the first dose of trial treatment and while participating in the trial. Examples of live vaccines include, but are not limited to, the following: measles, mumps, rubella, chicken pox, yellow fever, rabies, Bacillus Calmette-Guerin (BCG), and typhoid (oral) vaccine. Seasonal influenza vaccines for injection are generally killed virus vaccines and are allowed. However, intranasal influenza vaccines (eg, Flu - Mist[®]) are live attenuated vaccines, and are not allowed.
- any surgery for cancer (other than the exceptions noted in Section 6.6)

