## Best overall response (BOR) per Modified irRC-RECIST

Best overall response (BOR) of complete response (CR), partial response (PR), stable disease (SD), progressive disease (PD) or un-evaluable (UE) will be derived based on investigator assessment using modified irRC-RECIST as defined in protocol Appendix D.

Overall visit response assessments occurring after the start of the first subsequent anticancer therapy **will not be included. With the exception of a PD observation, the overall visit response** occurring on or after complete or partial removal/reduction of any target lesion which contained cancer on pathology evaluation or pathology results were unknown, will not be included. Consecutive confirmation of CR, PR, and PD is required where the second overall response must be at least 28 days from the first, the only exception being when the investigator reports that an initial PD cannot be confirmed due to rapid clinical deterioration. The following will be considered a confirmed PR: CR followed by PR or PR followed by CR.

BOR is defined as the best visit response in the following order: CR, PR, SD, PD, or UE (see [Table 1](#)). BOR is defined as SD if the best overall visit response is an unconfirmed CR or PR, and UE if it is either SD earlier than 77 days after first dose date or an unconfirmed PD when confirmation of PD is required (ie, initial PD without rapid clinical deterioration).

Table 1. Matrix of Determining BOR per Modified irRC-RECIST

Visit Overall Response Sequence	Examples	Best Overall Response	Confirmation specifications
*, CR, CR,*	PR, CR, CR CR, CR, PD	CR	The confirmatory CR must be at least 4 weeks (28 days) later; a subsequent CR within 28 days will not be valid for

			confirmation and will be ignored; the CR will also not be confirmed if there is a subsequent PR/SD/PD at any time prior to the next CR.
* , PR, PR, *  * , PR, CR/PR, non-CR, *  * ,CR, PR,*	PR, PR, PD PR, CR, PD  CR, PR, PD	PR	Criteria for BOR=CR not met. The confirmatory PR/CR must be no less than 4 weeks (28 days) later; a subsequent PR/CR within 28 days will not be valid for confirmation and will be ignored; the PR will also not be confirmed if there is a subsequent SD/PD at any time prior to the next PR/CR.
* , SD, *  * ,CR, non-PR/CR, *  * ,PR, non-PR/CR, *	CR PD, CR PR PD, PR, SD SD PD,SD,PD	SD	Criteria for BOR=CR or PR not met. SD must be $\geq 77$ days from the date of first dose; however, this is not required for an unconfirmed CR/PR.

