### **9. Statistical Methods of Analysis**

#### **9.1 General Considerations**

In Part 1, the efficacy and safety analyses will be conducted separately in monotherapy and combination cohorts. The DLT analysis set will be used to summarize the subject incidence of DLT for the study and the Safety Analysis Set will be used for all other analyses of safety endpoints (including but not limited to all adverse events, grade  $\geq 3$  adverse events, serious adverse events, fatal adverse events, adverse events requiring discontinuation of study drug, and AEs defined as events of interest). The efficacy analysis will be conducted using the Full Analysis Set unless otherwise specified. All the analysis may be conducted overall or by cohort/ group if appropriate.

In Part 2, the efficacy and safety analyses will be conducted separately by each tumor type arm. The efficacy analysis will be conducted using the Full Analysis Set unless

otherwise specified. The Safety Analysis Set will be used for all other analyses of safety endpoints.

In principle, mean, standard deviation, median, first and third quartiles, minimum and maximum will be calculated for continuous variables; frequency count and percent will be calculated for binary and categorical variables. The analysis of response variant endpoints will be based on investigator assessments per modified irRC-RECIST as described in the protocol unless otherwise specified.

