### **9.6.7 Exposure to Other Protocol-required Therapy**

Summary statistics for subjects in the Full Analysis Set who undergo on-protocol surgery including any surgery/procedure performed, type of procedure, and intent of surgery (e.g., palliative) will be provided.

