**10. Changes From Protocol-specified Analyses**

N/A

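### The SAP's PFS definition omits palliative radiation, which protocol 6.9 treats as progression for PFS, and SAP section 10 declares no change

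*SAP*

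**What the plan says.** **PFS events.** SAP section 5, under Progression-free survival, states: "PFS is defined as the interval from first dose date to the earlier event of confirmed PD or death from any cause". A subject with neither is censored at the last evaluable tumor assessment, or on Study Day 1 if there is none. Radiation appears in neither rule.

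**Radiation.** Protocol 6.9 states: "Administration of palliative radiation therapy will be considered clinical progression for the purposes of determining PFS". That sentence ends a note on radiation to a symptomatic solitary lesion or to the brain, which may be considered exceptionally and after consultation with the sponsor. Protocol 6.6 allows local palliative radiation for symptom relief at any time on study and attaches no PFS consequence. It adds: "Subjects with local symptoms suggestive of disease progression should be evaluated for tumor response per modified irRC-RECIST" before the radiation is given, and for subjects who are irradiated "the treatment should be recorded in the source document and CRF".

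**Declared changes.** SAP section 10, headed "Changes From Protocol-specified Analyses", contains only N/A. The SAP introduction says that it details the analyses of the protocol dated 26 October 2021, so this is not a difference between versions.

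**PD confirmation.** The SAP's BOR definition uses modified irRC-RECIST as in protocol Appendix D and requires PD to be confirmed, "the only exception being when the investigator reports that an initial PD cannot be confirmed due to rapid clinical deterioration". Appendix D waives confirmation in two situations: rapid clinical deterioration, and symptomatic disease that needs a rapid start of other systemic anticancer therapy. The imaging footnote to Tables 12 and 13 says the same.

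**The concern.** A subject given palliative radiation before any confirmed PD has a PFS event under protocol 6.9. Under the SAP the same subject stays at risk or is censored. Two programmers, one working from each document, would produce different Kaplan-Meier curves, and the SAP section meant to list departures would not explain why. The need for radiation is probably related to prognosis, so treating these subjects as event-free is unlikely to be neutral. The expected direction is a longer PFS.

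The confirmation wording raises a smaller concern of the same kind. A subject with one PD scan who changes therapy quickly because of symptoms has PD under Appendix D, but may not have PD under the SAP's single exception.

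**Working it through.** **Does any SAP text bring radiation back?** SAP 9.1 bases response endpoints on investigator assessment "per modified irRC-RECIST as described in the protocol unless otherwise specified", and the BOR definition points to Appendix D. The radiation rule is in protocol 6.9, not in Appendix D, so neither reference imports it.

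**Does the scope of 6.9 matter to the finding?**
- Broad reading (all palliative radiation under 6.6): the SAP omits all of it.
- Narrow reading (only the exceptional cases in the note): the SAP omits those.

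The mismatch exists either way. Only the number of subjects affected changes.

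**PD confirmation.** The SAP's BOR matrix (Table 1) treats PD with rapid clinical deterioration as PD without confirmation. The DOR definition refers back to that BOR rule; the PFS definition does not. Neither the matrix nor the BOR text names the symptomatic-disease waiver. Protocol 3.5.1 describes deterioration more broadly, including a need for other therapy, and may partly cover it.

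**Size.** The plan states no PFS figure to reproduce, and gives no frequency of radiation or of waived confirmations. What follows is an illustration on the protocol's scan schedule (week 10, then every 9 weeks). With day = (week − 1) × 7 and 30.44 days per month, weeks 10, 19 and 28 fall at 63, 126 and 189 days, or 2.1, 4.1 and 6.2 months.

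Assumed arm: 10 subjects, 4 events by week 12, 2 at week 19, 2 at week 28, and 2 event-free beyond that. At ties, events precede censorings.

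- All 4 early events counted: S(19) = 6/10 × 4/6 = 0.40; S(28) = 0.40 × 2/4 = 0.20.

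One early event is radiation at week 12 without confirmed PD, the other three occur by week 10, and the SAP rule is applied:

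| Irradiated subject under the SAP | S(19) | S(28) |
|---|---|---|
| Censored at week 10 | 7/10 × 4/6 = 0.467 | 0.467 × 2/4 = 0.233 |
| Censored at week 19 | 7/10 × 5/7 = 0.50 | 0.50 × 2/4 = 0.25 |
| Event-free to week 28 or later | 7/10 × 5/7 = 0.50 | 0.50 × 3/5 = 0.30 |

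The largest shift is 0.50 − 0.40 = 0.10 at week 19 and 0.30 − 0.20 = 0.10 at week 28. At these two scans it is zero if the evaluation before radiation shows PD that is later confirmed, because Appendix D dates progression to the first PD scan. It is also zero if the subject dies before week 19.

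Two affected subjects, both without a counted event until after week 28: S(19) = 8/10 × 6/8 = 0.60; S(28) = 0.60 × 4/6 = 0.40. The shift is 20 points at each scan.

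A week-10 PD whose waiver the SAP does not recognise behaves in the same way. If censored on that scan, one such subject gives 0.467 and 0.233. Two give 8/10 × 4/6 = 0.533 and 0.533 × 2/4 = 0.267. If both are instead counted only at deaths after week 28, the values are again 0.60 and 0.40.

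**A second model agrees in direction.** Suppose times are exponential, radiation is independent of PD and death, and a share r of first events under 6.9 is radiation. Dropping those events multiplies median PFS by 1/(1 − r): 1.05, 1.11 and 1.25 for r = 5%, 10% and 20%. These shares are also assumed.

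**The case against.** The strongest objection concerns scope. The 6.9 sentence sits in a note on exceptional radiation, and 6.6, the section that permits palliative radiation, names no PFS consequence. A reader might infer that every palliative course under 6.6 is a settled PFS event; the protocol does not establish that. This stands as a limit on how many subjects are affected. It does not remove the mismatch, because the SAP has no radiation event on the narrow reading either.

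A second objection is that an SAP may refine a protocol. It may, but section 10 is then the place to say so, and 6.9 should not continue to state the opposite.

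On confirmation, a reader might infer that the SAP censors PFS for subjects whose PD was exempt because of rapid deterioration. The more natural reading is that confirmed PD means PD meeting the BOR rule, which already accepts those cases, so the missing cross-reference is a matter of clarity. Nor has the SAP plainly discarded the second waiver: it also invokes Appendix D, and the broader wording in protocol 3.5.1 may cover part of it. The texts are inconsistent, but this point carries lower confidence than the radiation point.

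Finally, PFS is a secondary endpoint, summarized by Kaplan-Meier estimates without a test. That limits the consequence.

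**Conclusion.** The radiation point holds. The SAP's PFS event set is narrower than protocol 6.9 on any reading of 6.9, and the difference is not declared. The confirmation point is a real but narrower inconsistency in wording.

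PFS would tend to be overestimated. The actual amount cannot be derived from the documents. In the assumed arm of 10, the shift at weeks 19 and 28 is 0 to 10 points for one affected subject and up to 20 points for two. Those figures depend on the invented event pattern and on when the affected subjects are last scanned or die.

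A reader might infer that the trial's main conclusion is at risk. The documents do not support that. The primary analysis and the stage 1 futility rule count CR and PR, and a subject whose unconfirmed PD is classed as unevaluable is still a non-responder. ORR and the two-stage decisions do not change.

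**What to change.** 1. State in protocol 6.9 which radiation the sentence covers for PFS: only the cases in its note, or all local palliative radiation under 6.6. This settles the endpoint definition and takes no position on when radiation should be given.
2. Then either add that radiation as a PFS event in SAP section 5, with the event date defined, or declare its removal in SAP section 10 and correct 6.9.
3. Have the PFS definition refer to the BOR rule for PD, as DOR does. Align the BOR text and Table 1 with both waivers in Appendix D, and say how the wording in protocol 3.5.1 is to be read, so that BOR, DOR and PFS use one PD definition.

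The cost is mostly wording and programming. Radiation is already recorded on the CRF, and PD with rapid deterioration is already defined in Table 1. The documents show no separate field for the symptomatic-disease waiver, so those subjects may have to be identified from the subsequent-therapy data or by query. Reported PFS may become somewhat shorter.

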### **Treatment Period**

Treatment period is defined as the period between the first date of IP administration in the study and 30 days after the last IP administration in the study.

### **Subject Incidence of Detectable Talimogene Laherparepvec in Blood and Urine**

This endpoint is the prevalence of subjects with detectable talimogene laherparepvec DNA per qPCR in the blood /urine after the administration of talimogene laherparepvec within the first 4 cycles and safety follow-up per time point.

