- **Combination Cohorts:** the MTC of intrahepatic injection of talimogene laherparepvec into liver tumors in combination with systemic intravenous (IV) administration of pembrolizumab in subjects with non-HCC, and subjects with primary HCC with or without viral hepatitis

Part 2:

- To evaluate the efficacy, as assessed by objective response rate (ORR) of intratumoral injection of talimogene laherparepvec in combination with systemic IV administration of pembrolizumab, separately, for each non-HCC tumor type (hormone receptor positive breast adenocarcinoma [BC], triple negative breast cancer [TNBC], colorectal adenocarcinoma [CRC], cutaneous squamous cell carcinoma (CSCC)), basal cell carcinoma [BCC], as well as primary HCC with and without viral hepatitis.
- To evaluate safety separately for each tumor type as assessed by subject incidence of treatment-emergent and treatment-related adverse events, including DLTs

Secondary Objectives: The secondary objectives of the study are as follows:

EFFICACY:

Part 1:

To evaluate the efficacy separately by monotherapy versus combination for non-HCC tumors and HCC with and without viral hepatitis when applicable as assessed by:

- ORR, best overall response (BOR), durable response rate (DRR), duration of response (DOR), response in injected and uninjected lesions, disease control rate (DCR), progression-free survival (PFS), and overall survival (OS)
-

Part 2:

- To evaluate the efficacy in individual tumor types in the non-HCC group and HCC group with and without viral hepatitis as assessed by:
 - BOR, DRR, DOR, response in injected and uninjected lesions, DCR, PFS, and OS by primary tumor type (TNBC, Hormone receptor positive BC, CRC, CSCC, BCC, and HCC with and without viral hepatitis)

SAFETY (Parts 1 and 2)

- To evaluate the safety in each monotherapy and combination cohorts in Part 1 and each arm separately in Part 2, as assessed by subject incidence of treatment-emergent and treatment-related adverse events
- To estimate the incidence of detectable talimogene laherparepvec deoxyribonucleic acid (DNA) in blood and urine
- To estimate the incidence of clearance of talimogene laherparepvec DNA from blood and urine
- To estimate the rate of detection (per sample) and incidence (per subject) of talimogene laherparepvec DNA and virus at the surface of talimogene laherparepvec injection site, the exterior of occlusive dressing, and the oral mucosa

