10. STATISTICAL CONSIDERATIONS

10.1 Study Endpoints, Analysis Sets, and Covariates

10.1.1 Study Endpoints

Primary Endpoint:

Part 1:

Monotherapy cohorts 1-4: Subject incidence of DLTs with intrahepatic injection of talimogene laherparepvec into liver tumors in subjects with non-HCC with liver metastases and subjects with HCC without active viral hepatitis.

Combination cohorts 5 and 6: Subject incidence of DLTs with intrahepatic injection into liver tumors of talimogene laherparepvec in combination with systemic IV administration of pembrolizumab in subjects with non-HCC with liver metastases and subjects with HCC with and without viral hepatitis.

Part 2:

- ORR per modified irRC-RECIST with intralesional injection of talimogene laherparepvec into cutaneous, subcutaneous, lymph node, and liver tumors in combination with systemic IV administration of pembrolizumab separately by tumor type arm (hormone receptor positive BC, TNBC, CRC, CSCC, BCC, and HCC with and without viral hepatitis)
- Subject incidence, for each tumor type arm, of treatment-emergent and treatment-related adverse events, including DLTs

Secondary Endpoint(s):

Efficacy:

Part 1:

- ORR, BOR, DRR, DOR, response in injected and uninjected lesions, DCR, PFS, and OS separately for non-HCC and HCC tumors in monotherapy and combination cohorts

Part 2:

- BOR, DRR, DOR, response in injected and uninjected lesions, DCR, PFS, and OS by primary tumor type arm (hormone receptor positive BC, TNBC, CSCC, CRC, BCC, and HCC with and without viral hepatitis)

Safety:

Parts 1 and 2:

- Subject incidence of treatment-related and treatment-emergent adverse events in each monotherapy and combination cohorts in Part 1 and each tumor type separately in Part 2, and HCC with and without viral hepatitis in Part 2
- Subject incidence of detectable talimogene laherparepvec DNA in blood and urine

- Incidence of clearance of talimogene laherparepvec DNA from blood and urine
- Subject incidence (per subject) and rate of detection (per sample) of talimogene laherparepvec DNA and virus at the surface of injection site, the exterior of the occlusive dressing, and the oral mucosa
- Subject incidence of talimogene laherparepvec DNA detection in lesions suspected to be herpetic in origin

Exploratory Endpoint:

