### **Subject Incidence of Detectable Talimogene Laherparepvec in Blood and Urine**

The analysis will be based on the Blood Evaluable Analysis Set in which proportions of subjects that meet the criteria of detectable (defined as positive result by qPCR analysis) DNA in blood will be calculated. The point-wise exact 95% confidence intervals for binomial proportions using the F-distribution ([Leemis and Trivedi, et al, 1996](#)) from SAS® PROC FREQ procedure with the binomial option will also be calculated. Similar analysis of incidence of talimogene laherparepvec DNA detected in the urine will be repeated using the Urine Evaluable Analysis Set.

A detailed listing of qPCR results for subjects with detectable talimogene laherparepvec DNA per qPCR timepoints during the first 4 cycles and safety follow-up will be provided.

The analysis will be based on available cases; that is, subjects who do not have blood sample (or urine sample for respective analysis) collected at the respective time points will be excluded from the analysis for that time point.

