### **Rate and Subject Incidence of Talimogene Laherparepvec DNA Detection and Viral Detection on the Exterior of Occlusive Dressing**

The subject incidence of positive qPCR and subsequent positive plaque testings will be evaluated from swabs of occlusive dressings. The number and proportion of subjects who have at least 1 positive qPCR result from the exterior of occlusive dressing swabs and the number and proportion of subjects exhibiting detectable virus from subsequent plaque testings will be presented. Numeric results of positive qPCR, and separately for positive plaque analysis, will be summarized as a continuous variable.

A detailed listing of qPCR and subsequent plaque results for subjects having a positive qPCR testing will be provided.

The analysis of this endpoint will be based on the Exterior of Occlusive Dressing Evaluable Analysis Set.

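### The SAP reports detection of viral DNA in blood and urine as prevalence at each time point and specifies no any-time subject incidence, unlike its swab endpoints

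*SAP*

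**What the plan says.** The protocol's secondary safety objective (Synopsis and section 1.2) is "To estimate the incidence of detectable talimogene laherparepvec deoxyribonucleic acid (DNA) in blood and urine". The matching endpoint in protocol 10.1.1 is "Subject incidence of detectable talimogene laherparepvec DNA in blood and urine". Neither names a time point or a window, and neither says how many positive results make a subject positive.

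SAP section 5 keeps the heading of subject incidence but defines the measure as follows: "This endpoint is the prevalence of subjects with detectable talimogene laherparepvec DNA per qPCR", with the qualifier "within the first 4 cycles and safety follow-up per time point".

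SAP 9.6.2 names the Blood Evaluable Analysis Set as the population and gives the statistic thus: "proportions of subjects that meet the criteria of detectable (defined as positive result by qPCR analysis) DNA in blood will be calculated". That sentence names no time point. The next one does: "The point-wise exact 95% confidence intervals for binomial proportions using the F-distribution" are to be added. The section closes with an available-case rule, under which subjects without a sample "collected at the respective time points will be excluded from the analysis for that time point". Urine is handled the same way. A listing of results for positive subjects over the whole window is also planned.

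For the dressing swabs, SAP 9.6.2 specifies "The number and proportion of subjects who have at least 1 positive qPCR result from the exterior of occlusive dressing swabs". Injection-site and oral swabs get the same treatment, and suspected herpetic lesions are scored on a positive result in any swab. SAP section 10, on changes from protocol-specified analyses, reads N/A.

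**The concern.** The objective asks what share of treated subjects have viral DNA appear in blood or urine. A series of time-point prevalences does not answer that. It shows how detection rises and falls, but different subjects may be positive at different times, and the series alone does not reveal how many distinct subjects are involved.

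Elsewhere the SAP treats subject incidence as a per-subject, any-positive measure. Blood and urine are the exceptions, under the same endpoint name and without a declared change. Following the written rule, the report would carry a table headed subject incidence with no any-time proportion and no interval for one. At stake is whether a named secondary safety endpoint on biodistribution is estimated in the form the protocol appears to intend.

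**Working it through.** The plan states no expected detection rate, power or precision for this endpoint, so there is no figure to reproduce. The check has three parts.

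**1. Texts side by side**

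| Endpoint | Per-subject measure in SAP 9.6.2 | Per-time-point measure |
|---|---|---|
| Dressing, injection-site and oral swabs | At least one positive result | Rate per swab (SAP 5) |
| Suspected herpetic lesions | Positive in any swab | Rate per swab (SAP 5) |
| Blood, urine | None explicitly any-time | Prevalence of subjects (SAP 5), point-wise CI and available cases (SAP 9.6.2) |

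Protocol 10.1.1 makes the same distinction for swabs, separating a per-subject incidence from a per-sample rate. Nothing else planned fills the gap. The listing covers positive subjects only and gives no proportion or interval. The clearance sets (SAP 6.7) require a positive result and a later sample in the same cycle, and clearance is analysed by cycle.

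**2. How the two quantities relate**

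Let p_t be the proportion positive at time t. If the same subjects are sampled at every time:

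max p_t ≤ any-time incidence ≤ min(1, sum of p_t).

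Toy case with 20 subjects and three times: subjects 1–6 positive at the first, 5–8 at the second, 9–10 at the third. The prevalences are 6/20 = 30%, 4/20 = 20% and 2/20 = 10%. The any-time incidence is 10/20 = 50%.

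Under available-case denominators the left-hand inequality can fail. Suppose 20 subjects are evaluable, 8 are sampled at one time and 6 of those are positive, and nobody else is ever positive. The time-point figure is 6/8 = 75%; the any-time figure is 6/20 = 30%.

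**3. Illustrative size**

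Scheduled samples after the first dose, through cycle 4 and safety follow-up (protocol 7.2.2, 7.2.3.1 and the footnotes to Tables 8 to 13):

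- Part 1: week 1 seven, week 4 eight including pre-dose, week 7 two, week 10 one, safety visit one. 7 + 8 + 2 + 1 + 1 = 19.
- Part 2, no intrahepatic injection: 2 + 3 + 1 + 1 + 1 = 8. Intrahepatic injection adds the two 1-hour samples, giving 10.

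Assume the same prevalence p at each of k times with complete sampling. The bounds are p and min(1, kp); independence gives 1 − (1 − p)^k.

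| k | p | Bounds | If independent |
|---|---|---|---|
| 19 | 5% | 5% to 95% | 62% |
| 19 | 10% | 10% to 100% | 86.5% |
| 8 | 5% | 5% to 40% | 34% |
| 8 | 10% | 10% to 80% | 57% |
| 8 | 20% | 20% to 100% | 83% |

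Repeat samples from one subject are correlated. A probit random-effect model with flat 10% prevalence and latent correlation from 0.3 to 0.9 gives any-time incidence of 64% down to 23% for 19 samples, and 44% down to 20% for 8.

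Flat prevalence is an awkward assumption. Part 1 sampling is concentrated in the first 48 hours, and the SAP's clearance endpoint expects positive subjects to turn negative within a cycle. With an assumed early-peaked Part 1 profile (60% at the peak, 1–2% by day 14 and pre-dose), the same model gives 71% to 95%. That is 71/60 ≈ 1.2 to 95/60 ≈ 1.6 times the peak figure. Under flat 10% the ratio was 23/10 = 2.3 to 64/10 = 6.4. The gap therefore depends heavily on the time profile.

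**The case against.** Four objections deserve weight.

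- **The omission is not certain.** The main sentence in SAP 9.6.2 is not tied to a time point, its analysis set (SAP 6.6) needs only one post-dose sample, and the point-wise intervals come as an addition. A programmer could read it as an any-time proportion. This stands, so a reader who infers that the incidence will never be estimated goes too far. But the section 5 definition and the available-case rule both point the other way, and a plan open to both readings still needs settling.
- **The direction is not fixed.** A reader might infer that the reported figures must understate the incidence. The documents do not support that. Time-point prevalence is a different quantity, not a biased version of the same one, and the 75% against 30% case shows the order can reverse when sampling is incomplete.
- **The protocol wrote no at-least-one-positive rule here.** True. That reading is inferred from the term and from how the SAP treats every swab endpoint. The SAP filled a gap rather than contradicting a written definition.
- **Time-point reporting is not peculiar to blood and urine.** Also true: the SAP's swab rates are per time point too. The difference is that the swab endpoints have an any-time row as well.

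The endpoint is descriptive and carries no decision rule, which limits the consequence but does not remove the gap.

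**Conclusion.** The point holds as a gap between the stated definition and the objective. As written, SAP sections 5 and 9.6.2 lead to time-point prevalence in blood and urine and specify no any-time proportion with an interval. The swab endpoints have such a proportion, and section 10 records no departure from the protocol.

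The size cannot be computed from the documents. The ranges above rest on assumed prevalence, time profile and within-subject correlation, and on complete sampling; they show only that the two quantities can be close or far apart. The conclusion also rests on reading subject incidence as any-time, which the protocol implies but does not state. It is worth correcting because this is a named secondary safety endpoint and the data to answer it are already collected. No primary conclusion depends on it.

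**What to change.** In SAP section 5 and the matching part of 9.6.2, define subject incidence as the number and proportion of the Blood Evaluable Analysis Set (and separately the Urine set) with at least one positive post-dose qPCR within the first four cycles and safety follow-up. Give an exact 95% CI. Report it by part, because the schedules differ (19 samples against 8, or 10 with intrahepatic injection) and more samples give more chances of a positive. Keep the time-point table as a supporting summary and call it prevalence.

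The cost is one table row per matrix in each part and a short text edit. No new samples, data or analysis sets are needed.
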